9.2.2 Metabolic Change

In addition to mean change from baseline, incidence of treatment emergent significant changes in fasting lipids, fasting glucose, and metabolic syndrome will be summarized by treatment group using the following criteria.

Criteria for Treatment-Emergent Significant Change in Lipids and Glucose		
LAB PARAMETER	BASELINE ¹	ANYTIME POST BASELINE
LDL Direct, Fasting (MG/DL)	Borderline 100-<160	High >=160
	Normal/Borderline <160	High >=160
	Normal <100	Borderline/High >=100
	Any Value	Increased >=30
HDL Cholesterol, Fasting (MG/DL)	Normal >=40	Low <40
	Any Value	Decreased >=20
Triglycerides, Fasting (MG/DL)	Normal <150	High 200-<500
	Borderline 150-<200	High 200-<500
	Normal/Borderline <200	High 200-<500
	Normal <150	Borderline/High/Very High >=150
	Any Value	Increased >=50
Glucose Fasting, Serum (MG/DL)	Normal <100	High >=126
	Impaired 100-<126	High >=126
	Normal/Impaired <126	High >=126
	Any Value	Increased >=10

¹ BASELINE IS CALCULATED FROM WEEK 1.

Criteria for Treatment-Emergent Metabolic Syndrome	
DESCRIPTION	ANYTIME POST BASELINE ¹
Central Obesity	Waist Circumference >=102cm(MALE), >=88cm (FEMALE)
Dyslipidemia	Triglycerides >= 150mg/dl
Dyslipidemia	HDL < 40mg/dl (MALE), <50mg/dl (FEMALE)
Supine Blood Pressure	Systolic >=130mmHg and Diastolic >=85mmHg
Glucose Fasting, Serum	>=100mg/dl
Metabolic Syndrome	Met 3 Or More of the Above Criteria at a Visit

¹ BASELINE IS CALCULATED FROM WEEK 1.

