Appendix 2 Criteria for Identifying Laboratory Values of Potential Clinical Relevance

Laboratory Tests		Criteria
Chemistry		
AST (SGOT)		$\geq 3 \times$ upper limit of normal (ULN)
ALT (SGPT)		$\geq 3 \times$ ULN
Alkaline phosphatase		$\geq 3 \times$ ULN
Lactate dehydrogenase (LDH)		$\geq 3 \times$ ULN
Blood urea nitrogen (BUN)		≥ 30 mg/dL
Creatinine		≥ 2.0 mg/dL
Uric Acid		
Men		≥ 10.5 mg/dL
Women		≥ 8.5 mg/dL
Bilirubin (total)		≥ 2.0 mg/dL
Creatine phosphokinase (CPK)		$\geq 3 \times$ ULN
Prolactin		$>$ ULN
Hematology		
Hematocrit		
Men		$\leq 37\%$ and decrease of ≥ 3 percentage points from Baseline
Women		$\leq 32\%$ and decrease of ≥ 3 percentage points from Baseline
Hemoglobin		
Men		≤ 11.5 g/dL
Women		≤ 9.5 g/dL
White blood count		$\leq 2,800/\text{mm}^3$ or $\geq 16,000/\text{mm}^3$
Eosinophils		$\geq 10\%$
Neutrophils		$\leq 15\%$
Absolute neutrophil count		$\leq 1,000/\text{mm}^3$
Platelet count		$\leq 75,000/\text{mm}^3$ or $\geq 700,000/\text{mm}^3$
Urinalysis		
Protein		Increase of ≥ 2 units
Glucose		Increase of ≥ 2 units
Casts		Increase of ≥ 2 units
Additional Criteria		
Chloride		≤ 90 mEq/L or ≥ 118 mEq/L
Potassium		≤ 2.5 mEq/L or ≥ 6.5 mEq/L
Sodium		≤ 126 mEq/L or ≥ 156 mEq/L
Calcium		≤ 8.2 mg/dL or ≥ 12 mg/dL
Glucose		
Fasting		≥ 100 mg/dL
Non-Fasting		≥ 200 mg/dL
Total Cholesterol, Fasting		≥ 240 mg/dL
LDL Cholesterol, Fasting		≥ 160 mg/dL
HDL Cholesterol, Fasting		
Men		< 40 mg/dL
Women		< 50 mg/dL
Triglycerides, Fasting		≥ 150 mg/dL

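### The triglyceride shift-to-high rows in SAP 9.2.2 stop at 500 mg/dL, so a move from below 200 to 500 or more is not counted although a smaller worsening is.

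*SAP*

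**What the plan says.** The first criteria table in SAP 9.2.2 has five triglyceride rows. Three count a shift to high and share one bounded outcome:

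- "Normal <150 High 200-<500"
- "Borderline 150-<200 High 200-<500"
- "Normal/Borderline <200 High 200-<500"

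The fourth row starts from a baseline below 150 and has the open-ended outcome "Borderline/High/Very High >=150". The fifth applies to any baseline: "Increased >=50".

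In the same table, LDL is open-ended ("Normal/Borderline <160 High >=160"), and so is glucose ("Normal/Impaired <126 High >=126"). Any post-baseline value may qualify, and incidence is reported by treatment group. Protocol Table 3.7-1 schedules the clinical laboratory tests at screening and at Day 21/ET, so there is one scheduled post-baseline lipid value per subject.

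**The concern.** A shift-to-high count should not fall as the subject gets worse. With the cap in place, a value of 499 is an event and a value of 500 from the same baseline is not. The fourth triglyceride row shows that the SAP recognises a Very High class above High, yet no row counts a shift into that class on its own. What is at stake is the accuracy of a by-arm metabolic safety incidence table for an antipsychotic, in a trial whose secondary objective is safety and tolerability. The primary and key secondary analyses do not use this table.

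**Working it through.** The plan states no figure to reproduce, so the check is logical, followed by a rough size.

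**Step 1: apply the printed rows.** Write b for baseline and p for the post-baseline value in mg/dL. The rules are:

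- R1: b < 150 and 200 ≤ p < 500
- R2: 150 ≤ b < 200 and 200 ≤ p < 500
- R3: b < 200 and 200 ≤ p < 500
- R4: b < 150 and p ≥ 150
- R5: p − b ≥ 50

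| b | p | Shift-to-high rows met (R1–R3) | Other rows met |
|---|---|---|---|
| 120 | 499 | R1, R3 | R4, R5 |
| 120 | 500 or 650 | none | R4, R5 |
| 180 | 499 | R2, R3 | R5 |
| 180 | 500 or 650 | none | R5 |
| 190 | 210 | R2, R3 | none (rise of 20) |
| 190 | 510 | none | R5 (rise of 320) |

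**Step 2: compare with open-ended rows.** R3 was compared with its open-ended form (b < 200 and p ≥ 200) over all integer pairs with b from 30 to 199 and p from 30 to 1500. The two differ only where p ≥ 500 and agree at every value below 500. Every pair that R3 misses meets R5, because p − b is at least 500 − 199 = 301. Pairs with b < 150 also meet R4; pairs with b from 150 to 199 do not.

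**Step 3: more than one post-baseline value.** Since any post-baseline value qualifies, a subject with b = 150 and values of 300 and 600 is counted through the 300. With 600 alone the subject is not counted. A second value needs an unscheduled sample.

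**Step 4: size, on assumptions.** None of these inputs is in the documents except 152, the planned evaluable number per arm. Fasting triglycerides are taken as log-normal with median 120 to 160 mg/dL, between-subject log-SD 0.45 to 0.60, within-subject log-SD 0.20 to 0.30, and a post-baseline shift of 0 to 0.10 on the log scale. Baseline and post-baseline logs are then bivariate normal, with variance equal to the sum of the two squared SDs and covariance equal to the squared between-subject SD.

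- Missed by the cap: 152 × P(b < 200, p ≥ 500) = about 0.001 to 0.26 subjects per arm.
- All shifts to 200 or more: 152 × P(b < 200, p ≥ 200) = about 8 to 24 subjects per arm.
- The missed share is about 0.01% to 1.3% of the open-ended count. The upper end needs all four assumptions at their maximum (0.26 / 19.8 = 1.3%).

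**The case against.** The strongest reply is that High and Very High are separate classes, so bounding High is coherent coding. Triglycerides are the only analyte in this table with a named class above High. That may be the intent, but a row for the shift to Very High is then missing, and the gap is the same. SAP 9.4 shows the complete pattern: its bounded QTc increase of 30 to 60 msec is followed by a row for more than 60. The list of summary tables in SAP section 13 is blacked out, so a further tabulation there can be neither confirmed nor excluded. The criteria printed in 9.2.2 remain incomplete either way.

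The second reply is that other outputs show these subjects, and this largely stands. They meet the rise of at least 50, and the fourth row if baseline was below 150. They enter mean change in full. Appendix 2 flags fasting triglycerides of 150 or more with no upper limit, and SAP 9.2 has those values summarised by group and listed. The metabolic syndrome criterion is also uncapped. A reader might infer that the plan hides the largest triglyceride rises; the documents do not support that. The narrower gap is that none of the categorical criteria separates a shift to 500 or more from a much smaller change.

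A reader might also blame the cap for a subject who goes from 300 to 600 and meets no shift row. That does not follow. A baseline of 200 or more is outside every shift-to-high row whatever its upper limit, and the LDL and glucose rows treat subjects already high at baseline in the same way.

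**Conclusion.** The three rows are wrong as written, in a limited way. A subject who moves from below 200 to 500 mg/dL or more on the single scheduled post-baseline draw is left out of the shift-to-high incidence, while a smaller worsening from the same baseline is counted. That follows from the printed rows and the visit schedule and needs no assumption beyond the absence of a qualifying unscheduled value.

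The expected number is under one subject per arm. That size rests wholly on the assumed distributions, so it indicates order of magnitude only. The table is descriptive, with no test attached, and no efficacy conclusion is affected. The correction is worth making because the rule miscounts the most extreme worsening and costs almost nothing to repair.

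**What to change.** In SAP 9.2.2, replace the bounded outcome in the three triglyceride shift-to-high rows with High/Very High at 200 mg/dL or more, in line with the LDL and glucose rows. If High is meant as a closed class, keep the three rows and add one from baseline below 200 to Very High at 500 or more. A row from any baseline below 500 to 500 or more is optional. It would also pick up subjects already high at baseline, but the defect does not require it.

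The cost is three changed cells or one added row, plus the matching table program. No new data and no protocol change are needed. Opening the three rows alters no count for values below 500. The downside for the sponsor is that the reported triglyceride shift rates may become slightly less favourable.

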18.	
Subjects with uncontrolled hypertension (DBP > 95 mmHg in any position) or symptomatic hypotension, or orthostatic hypotension which is defined as a decrease of ≥ 30 mmHg in SBP and/or a decrease of ≥ 20 mmHg in DBP after at least 3 minutes standing compared to the previous supine blood pressure, OR development of symptoms.
 
NOTE: Blood pressure measurements may be repeated once to ensure reproducibility of the exclusionary result(s) before excluding a subject based on the criteria noted above.

19.	Subjects with epilepsy or a history of seizures, except for a single seizure episode; for instance childhood febrile, post traumatic, or alcohol withdrawal seizure.
20.	Subjects with a history of a gastric bypass surgery that creates a malabsorptive state, including Roux-en-Y gastric bypass and biliopancreatic bypass with duodenal switch. This does not include gastric banding, gastric stapling, and sleeve gastrectomy procedures.

Table 3.4.3-1 Exclusion Criteria	
	Physical and Laboratory Results
21.	
Subjects with abnormal laboratory tests results, vital signs results, or ECG findings, unless, based on the investigator's judgment, the findings are not medically significant and would not impact the safety of the subject or the interpretation of the trial results. The medical monitor should be contacted to discuss individual cases, as needed. Criteria are provided in Section 3.7.3.2. In addition, subjects with the following laboratory test and ECG results at screening must be excluded from the trial:
 
 • Platelets $\leq 75000/\text{mm}^3$ • Hemoglobin $\leq 9 \text{ g/dL}$ • Neutrophils, absolute $\leq 1000/\text{mm}^3$ • AST $> 2 \times \text{ULN}$ • ALT $> 2 \times \text{ULN}$ • CPK $> 3 \times \text{ULN}$, unless discussed with and approved by the medical monitor • Creatinine $\geq 2 \text{ mg/dL}$ • QTcF $\geq 450 \text{ msec}$ in men and $\geq 470 \text{ msec}$ in women, unless due to ventricular pacing. 
Tests with exclusionary results should be repeated to ensure reproducibility of the abnormality before excluding a subject based on the criteria noted above. For ECG, perform 3 consecutive recordings. If 2 of the 3 remain exclusionary then the subject must be excluded.

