Appendix 1 Criteria for Identifying Vital Signs of Potential Clinical Relevance

Variable	Criterion Value ^a	Change Relative to Baseline ^a
Heart Rate ^b	> 120 bpm < 50 bpm	≥ 15 bpm increase ≥ 15 bpm decrease
Systolic Blood Pressure ^b	> 180 mmHg < 90 mmHg	≥ 20 mmHg increase ≥ 20 mmHg decrease
Diastolic Blood Pressure ^b	> 105 mmHg < 50 mmHg	≥ 15 mmHg increase ≥ 15 mmHg decrease
Orthostatic Hypotension	≥ 20 mmHg decrease in systolic blood pressure and a ≥ 25 bpm increase in heart rate from supine to sitting/standing	Not Applicable (baseline status not considered)
Weight	-	≥ 7% increase ≥ 7% decrease

^a In order to be identified as potentially clinically relevant, an on-treatment value must meet the “Criterion Value” and also represent a change from the subject’s baseline value of at least the magnitude shown in the “Change Relative to Baseline” column.

^b As defined in “Supplementary Suggestions for Preparing an Integrated Summary of Safety Information in an Original NDA Submission and for Organizing Information in Periodic Safety Updates,” FDA Division of Neuropharmacological Drug Products draft (2/27/87).

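### The metabolic-syndrome blood-pressure component needs both pressures raised, so a subject with one raised pressure and exactly two other components is not classed as having the syndrome

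*SAP*

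**What the plan says.** SAP 9.2.2 states that the incidence of treatment-emergent significant changes in fasting lipids, fasting glucose and "metabolic syndrome will be summarized by treatment group using the following criteria". The metabolic-syndrome table has five components:

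- waist circumference at or above 102 cm (men) or 88 cm (women);
- "Triglycerides >= 150mg/dl";
- HDL below 40 mg/dL (men) or 50 mg/dL (women);
- supine blood pressure, "Systolic >=130mmHg and Diastolic >=85mmHg";
- fasting glucose at or above 100 mg/dL.

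The classification rule is "Met 3 Or More of the Above Criteria at a Visit". The table has one criteria column, headed as any time post baseline, and a footnote on where baseline comes from. It does not say whether subjects who already meet the syndrome at baseline are removed. No footnote or other section turns the blood-pressure *and* into *or*. The protocol contains no metabolic-syndrome definition, and neither document cites a source for the cut-offs.

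**The concern.** The blood-pressure row is the only one of the five that asks for two abnormalities at once. The two lipid abnormalities sit in separate rows and each counts alone. The joint condition also orders severity oddly, since a reading exactly at both thresholds qualifies while a much higher systolic pressure with a diastolic of 84 does not.

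Usage elsewhere points the same way. Where either pressure is enough, the protocol writes *and/or* (orthostatic hypotension, Exclusion 18 in Table 3.4.3-1). SAP Appendix 1 gives systolic and diastolic pressure separate rows. Where Appendix 1 does use *and* (a systolic fall with a heart-rate rise), it means both. A programmer will therefore most naturally code the row as a joint condition.

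At stake is the reported incidence of metabolic syndrome in a descriptive safety table, and the table's ability to show a treatment difference that arises mainly through one of the two pressures.

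**Working it through.** The documents state no expected metabolic-syndrome rate, so there is no figure of the plan to reproduce.

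**Step 1: apply the rule literally.**

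| Supine reading (mmHg) | Both required (SAP) | Either sufficient |
|---|---|---|
| 130/85 | met | met |
| 160/80 | not met | met |
| 179/84 | not met | met |
| 128/95 | not met | met |

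SAP Appendix 1 flags high values only above 180 systolic or 105 diastolic, each with a minimum rise from baseline, so it does not pick up the last three readings either. Exclusion 18 removes a diastolic above 95 but sets no upper systolic limit, so isolated systolic elevation is not screened out.

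**Step 2: who is affected.** Let K be the number of the other four components met, and b the probability that the blood-pressure component is met. Taking K and blood pressure as independent:

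P(syndrome) = P(K ≥ 3) + P(K = 2) × b

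Only subjects with K = 2 can change class. At one visit, P(both raised) cannot exceed P(at least one raised), so the direction is certain for a post-baseline count.

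**Step 3: cross-sectional size (assumed inputs).** Other components: 0.45, 0.32, 0.40 and 0.30, independent. Then P(K = 2) = 0.327 and P(K ≥ 3) = 0.124 + 0.017 = 0.141. Blood pressure: bivariate normal, SBP SD 13–15, DBP SD 9–10.

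| SBP/DBP mean, correlation | b, *and* | b, *or* | Syndrome, *and* | Syndrome, *or* |
|---|---|---|---|---|
| 120/77, 0.60 | 0.101 | 0.307 | 0.141 + 0.327 × 0.101 = 17.4% | 24.2% |
| 125/79, 0.60 | 0.182 | 0.452 | 20.1% | 28.9% |
| 125/79, 0.75 | 0.209 | 0.425 | 21.0% | 28.0% |
| 130/81, 0.65 | 0.275 | 0.570 | 23.1% | 32.8% |

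The gap is 0.327 × (difference in b), from 0.327 × 0.206 = 6.7 points to 0.327 × 0.295 = 9.6 points. That is about 11 to 15 subjects if all 160 in an arm had Day 21 data.

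**Step 4: other inputs.** A second grid (SBP mean 118–126, SD 13; DBP mean 74–80, SD 9; correlation 0.5–0.7; other components from 20–30% up to 40–55%) gives a gap of about 5 to 19 subjects per 160. At the middle of that grid, correlating the components at 0.2 to 0.4 gives about 10 to 11 per 160.

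**Step 5: new-onset size.** If subjects positive at baseline are removed, the *or* rule also finds more positives at baseline. I simulated two visits with the Step 3 inputs and an assumed between-visit correlation of 0.5 to 0.85. Moving from *and* to *or* raises new-onset cases by about 2 to 3 points of all subjects, or about 3 to 7 points of those negative at baseline.

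**The case against.** The strongest objection is that the documents cite no definition of metabolic syndrome. Under-reporting therefore has meaning only against an either-pressure comparator that has to be inferred. This stands: the texts cannot show that the sponsor departed from its source, and the fix must leave room for the sponsor to confirm that both pressures are meant.

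Several further points stand.

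- Appendix 1 and Exclusion 18 serve other purposes. They show how the documents word such rules, but they do not contradict 9.2.2.
- The *and* may be loose drafting. The QTc category label in SAP 9.4 joins the male and female limits with *and*, where *or* is meant. There, however, the definition beside the label spells out *or*. The blood-pressure row has no such clarification, and both pressures belong to the same subject.
- The table concerns treatment-emergent syndrome, so the cross-sectional gap is not necessarily the gap that would be reported. With baseline positives removed, a subject with isolated systolic elevation and two other components at baseline, who has both pressures raised later, can be a new case under *and* but not under *or*. The certain ordering in Step 2 then no longer applies, and the gain is much smaller.
- Mean changes in vital signs are summarized by arm (SAP 9.3). This softens the consequence, but it does not supply the incidence that the component is meant to give.

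A reader might infer that the rule makes brexpiprazole look safer. The documents do not support that, because the same rule applies to both arms. A reader might also infer that everyone with a single raised pressure is lost to the syndrome count. That is wrong too: three of the other four components are enough.

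**Conclusion.** The defect holds as a matter of text, and its direction is certain for a post-baseline count compared with an either-pressure rule: lower incidence in both arms, through subjects with one raised pressure and exactly two other components. It can mask a difference driven by one pressure. It does not by itself favour an arm, and it leaves the primary and key secondary analyses, alpha and power unaffected.

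The size is illustrative. Under the Step 3 assumptions it is about 17–23% versus 24–33% cross-sectionally. If baseline positives are removed, it is about 2 to 3 points of all subjects. Which scale applies depends on a baseline rule that SAP 9.2.2 does not state. Fasting laboratory tests and waist circumference are scheduled only at screening and Day 21/early termination (Protocol Table 3.7-1 and footnotes), so there is normally one post-baseline visit at which all five components are available. The point deserves correction, but it is not evidence of a biased treatment comparison.

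**What to change.** Before unblinding, change the analysis row in SAP 9.2.2 to *Systolic >=130 mmHg or Diastolic >=85 mmHg (supine)*, cite the definition from which the cut-offs were taken, and rerun the component and 3-of-5 counts. If the sponsor confirms that both pressures are intended, state this in the table and add an either-pressure count alongside. In the same edit, say whether subjects who meet the syndrome at baseline are removed.

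The cost is one word in the SAP, one logical operator in the program and a rerun of one descriptive table. Reported incidence is expected to rise somewhat in both arms.

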3.7 Trial Procedures

This trial is a phase 3, double-blind, placebo-controlled trial to investigate the efficacy, safety, and tolerability of brexpiprazole (2-4 mg/day) for the treatment of subjects with bipolar I disorder experiencing a manic episode with or without mixed features. The trial comprises a 3-week, double-blind treatment period with a 21 (\pm 2) day follow-up.

Trial assessment time points are summarized in Table 3.7-1.

Table 3.7-1 Schedule of Assessments							
	Screening ^a	Double-blind Treatment Phase					Follow-up ^c
	Day -14 to -1	Baseline (Day 1)	Day 4 (± 1 day)	Day 7 (± 1 day)	Day 14 (± 1 day)	Day 21/ET ^b (± 2 day)	21 (± 2) days after last dose
Screening Assessments and Randomization							
Informed Consent ^d	X						
Demographics	X						
Medical History	X						
Psychiatric History	X						
MINI	X						
Concomitant Medications ^e	X	X	X	X	X	X	X
Inclusion/Exclusion Criteria	X	X					
Randomization		X					
Efficacy Assessments							
YMRS ^f	X	X	X	X	X	X	
CGI-BP ^g		X	X	X	X	X	
CCI	█	█			█	█	
		█				█	
Safety Assessments							
Physical Examination ^h	X					X	
Vital Signs ⁱ	X	X	X	X	X	X	
Body Weight	X					X	
12-lead ECG ^j	X	X				X	
Clinical laboratory tests (hematology, serum chemistry, urinalysis), including prolactin ^k	X					X	
HbA1c ^j	X					X	

Table 3.7-1 Schedule of Assessments							
	Screening ^a	Double-blind Treatment Phase					Follow-up ^c
	Day -14 to -1	Baseline (Day 1)	Day 4 (± 1 day)	Day 7 (± 1 day)	Day 14 (± 1 day)	Day 21/ET ^b (± 2 day)	21 (± 2) days after last dose
TSH, with reflex to T ₄ if TSH is abnormal	X					X	
Coagulation parameters (PT, aPTT, INR) ^k	X					X	
Lithium, Valproate, Carbamazepine Levels ^l	X						
HIV, HBsAg, and anti-HCV	X						
Pregnancy Test ^m	X		X			X	
Drug Screen ⁿ	X					X	
Blood Alcohol Test ^o	X					X	
C-SSRS ^p	X	X	X	X	X	X	
CCI							
AEs ^q	X	X	X	X	X	X	X
CCI							
Other							
IMP dispensing ^s		X	X	X	X		
IMP accountability			X	X	X	X	

aPTT = activated partial thromboplastin time; HBsAg = Hepatitis B surface antigen; Anti-HCV = Antibodies to hepatitis C virus; INR = International Normalized Ratio; T₄ = free thyroxine; TSH = thyroid-stimulating hormone.

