7.1 Baseline Definition

For analyses of the double-blind treatment period data, the baseline is the Baseline measurement (expected to be at Day 1). Baseline measurement is defined as the last available measurement prior to the start of double-blind IMP.

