7.2 Demographic Characteristics

Baseline demographic characteristics include age, sex, race, ethnicity, height, weight, waist circumference, and body mass index (BMI). For the Randomized Sample, demographic characteristics will be summarized by treatment group.

Mean, range and standard deviation will be used to describe continuous variables such as age. Frequency distributions will be tabulated for categorical variables such as race.

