9.3 Vital Signs

Summary statistics for vital signs will be provided. For the double-blind treatment period, vital signs, change from baseline will be summarized for the Safety Sample by treatment group.

Potentially clinically relevant vital signs measurements identified in the double-blind treatment period for the Safety Sample will be summarized by treatment group. Criteria for identifying vital signs of potential clinical relevance are provided in [Appendix 1](#). All potentially clinically relevant events or changes will be listed and included in summary tables.

9.4 12-Lead ECG

Summary statistics and incidence of potentially clinically relevant changes will be provided for ECG parameters.

For the analysis of QT and QTc, data from three consecutive complexes (representing three consecutive heart beats) will be measured to determine average values. The following QT corrections will be used for reporting purposes in the clinical study report:

- 1) QTcB is the length of the QT interval corrected for heart rate by the Bazett formula:

$$QTcB=QT/(RR)^{0.5}$$
 and
- 2) QTcF is the length of the QT interval corrected for heart rate by the Fridericia formula:

$$QTcF=QT/(RR)^{0.33}$$
- 3) QTcN is the length of the QT interval corrected for heart rate by the FDA Neuropharm Division formula: $QTcN=QT/(RR)^{0.37}$

Potentially clinically relevant changes in the 12-lead ECG identified in the double-blind treatment period for the Safety Sample will be listed and summarized by treatment group. Criteria for identifying ECG measurements of potential clinical relevance are provided in [Appendix 3](#).

Categorical changes in ECG parameters during the double-blind treatment period will be summarized based on the following criteria:

Categorical Change Criteria in QT/QTc Parameters		
Classification	Category	Criteria
QT	New Onset (> 450 Msec)	New onset (>450 msec) in QT means a subject who attains a value > 450 msec during treatment period but not at baseline.
QTc *	New Onset (≥ 450 Msec for men and ≥ 470 Msec for women)	New onset (≥ 450 Msec for men and ≥ 470 Msec for women) in QTc means a subject who attains a

Categorical Change Criteria in QT/QTc Parameters		
Classification	Category	Criteria
	for women)	value \geq 450 Msec for men or \geq 470 Msec for women during treatment period but not at baseline.

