9.6 CCI

9.7 Suicidality Data

Suicidality will be monitored during the study using the C-SSRS and will be summarized as number and percentage of subjects reporting any suicidal behavior, ideation, behavior by type (4 types), ideation by type (5 types) and treatment emergent suicidal behavior and ideation. Summary will be provided for the double-blind treatment period.

Suicidality is defined as report of at least one occurrence of any type of suicidal ideation or at least one occurrence of any type of suicidal behavior during assessment period (count each person only once).

Treatment emergent suicidal behavior and ideation is summarized by four types: Emergence of suicidal ideation, Emergence of serious suicidal ideation, Worsening of suicidal ideation, Emergence of suicidal behavior.

Emergence of suicidal behavior/ideation is defined as report of any type of suicidal behavior/ideation during treatment when there was no baseline suicidal behavior/ideation.

Emergence of serious suicidal ideation is defined as observation of suicidal ideation severity rating of 4 or 5 during treatment when there was no baseline suicidal ideation.

Worsening of suicidal ideation is defined as a suicidal ideation severity rating that is more severe than it was at baseline.

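### The readable text of SAP 9.2.2 sets no baseline condition for treatment-emergent metabolic syndrome, so followed as written it counts unchanged pre-existing cases as emergent

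*SAP*

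**What the plan says.** The opening sentence of SAP 9.2.2 commits to this: "incidence of treatment emergent significant changes in fasting lipids, fasting glucose, and metabolic syndrome will be summarized by treatment group", using the criteria in two tables that follow.

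- **Lipid and glucose table.** Each row pairs a baseline entry with a post-baseline value.
- **Metabolic syndrome table.** It is titled as treatment-emergent but has only a description column and a column for any time after baseline. Five component rows (waist, triglycerides, HDL, supine blood pressure, fasting glucose) are followed by the case rule: "Met 3 Or More of the Above Criteria at a Visit".
- **Footnote to both tables.** "BASELINE IS CALCULATED FROM WEEK 1".

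SAP 7.1 defines baseline differently: "Baseline measurement is defined as the last available measurement prior to the start of double-blind IMP". SAP 9 gives the same rule for safety variables in general, while allowing exceptions.

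Two other SAP sections state what new onset means. For QT, SAP 9.4 says it "means a subject who attains a value > 450 msec during treatment period but not at baseline". For suicidality, SAP 9.7 counts emergence "during treatment when there was no baseline suicidal behavior/ideation".

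**The concern.** An emergent event should be one that was absent before treatment. The syndrome table carries that label, but its operative rule looks only at post-baseline values. A programmer who codes the table literally will report post-baseline prevalence under an incidence title.

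Pre-existing cases can be enrolled. Exclusion criterion 17 in the protocol admits stable non-insulin-dependent diabetes with fasting glucose up to 125 mg/dL, against a syndrome cut-off of 100. Criterion 18 excludes diastolic pressure only above 95 mmHg, against a syndrome cut-off of 85 (together with systolic 130). No exclusion criterion names triglycerides, HDL or waist circumference.

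Safety and tolerability are the secondary objective. At stake is whether this one table can show what three weeks of treatment added.

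**Working it through.** The documents give no figure for metabolic syndrome, so there is nothing to reproduce. The check is of the rule, followed by illustrations on assumed inputs.

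**1. Which rows condition on baseline.** Rows in the lipid and glucose table that restrict the baseline class: LDL 3 of 4, HDL 1 of 2, triglycerides 4 of 5, glucose 3 of 4. That is 3 + 1 + 4 + 3 = 11 of 15. The other 4 accept any baseline value but require a stated size of change. In the syndrome table, 0 of 6 rows do either.

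**2. The rule applied to an unchanged subject.** Take a hypothetical man with the same values at screening and Day 21: waist 108 cm (cut-off 102, met), triglycerides 190 mg/dL (150, met), HDL 36 mg/dL (below 40, met), supine blood pressure 124/78 (130 and 85, not met), fasting glucose 104 mg/dL (100, met). He meets 4 of 5 criteria both times. Under the written rule he is emergent, because 4 ≥ 3 after baseline. With an added condition of fewer than 3 at baseline he is not.

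**3. Whether baseline status is available.** Protocol Table 3.7-1 schedules the row "Clinical laboratory tests (hematology, serum chemistry, urinalysis), including prolactin" at Screening and Day 21/ET only. Waist follows the same two visits. Blood pressure is taken at Screening and again on Day 1. All five components therefore have a scheduled pre-dose value, but on different days: Day 1 alone supplies 1 of 5. SAP 9.9 defines Week 1 as Days 1 to 7 of dosing. Read that way, the footnote leaves triglycerides, HDL, glucose and waist with no scheduled baseline value.

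**4. Direction, equal persistence.** Let n be the pre-existing cases per arm that persist. Reported counts are new cases + n, so both arms rise. All inputs here are assumed: 8 vs 16 new cases.

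| n per arm | Reported | Excess | Ratio (16+n)/(8+n) |
|---|---|---|---|
| 0 | 8 vs 16 | 8 | 2.00 |
| 10 | 18 vs 26 | 8 | 1.44 |
| 30 | 38 vs 46 | 8 | 1.21 |
| 60 | 68 vs 76 | 8 | 1.12 |

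**5. Direction, unequal persistence (also assumed).** With 8 vs 10 new cases and 10 vs 20 persistent ones, the table shows 18 vs 30: the ratio rises from 1.25 to 1.67 and the excess from 2 to 12. With 8 vs 16 new cases and 20 vs 10 persistent ones, it shows 28 vs 26: a true excess of 8 becomes a deficit of 2.

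**6. How easily chance produces an imbalance.** With 160 per arm, assumed prevalence p and full persistence, the difference between arms in pre-existing cases has SD √(2 × 160 × p × (1 − p)). For p = 10% this is √28.8 = 5.4; for p = 40% it is √76.8 = 8.8.

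**The case against.** The strongest reply is that new onset is plainly intended. The opening sentence speaks of changes, the title says treatment-emergent, and a baseline footnote would be pointless if baseline played no part. The list of summary tables in SAP 13 is redacted and may carry a population note. Other outputs would still show a metabolic shift: mean changes from baseline, the lipid and glucose table, vital-sign changes (SAP 9.3), waist (SAP 9.5.1), and the laboratory summaries and listings under SAP 9.2.

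Much of this stands. A reader might infer that the sponsor chose to count pre-existing cases; the documents do not support that, and an omission is the likelier explanation. The redaction limits the claim to the readable text. The other outputs keep the consequence small. But intent does not supply the rule: the opening sentence defers to the listed criteria, and those leave both the baseline exclusion and the denominator unstated.

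A reader might also infer from the footnote that an on-treatment baseline was adopted, since SAP 9 permits exceptions. The schedule argues against this: no lipid, glucose or waist value is planned on Day 1, 4 or 7, so a label slip is more probable.

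**Conclusion.** The point holds for the readable text: as written, the rule counts persistent pre-existing metabolic syndrome as treatment-emergent. It raises the reported count in both arms by the number of such cases.

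A reader might go further and conclude that the ratio between arms is always diluted. It is not. Movement toward 1 requires similar numbers of persistent pre-existing cases in the two arms; with unequal numbers the error can go either way. If the numbers are equal, the excess count is unchanged.

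The size cannot be estimated, because the documents give neither a baseline prevalence nor an incidence; every number in steps 4 to 6 of the working rests on assumed inputs except the 160 per arm. The primary and key secondary analyses and their type I error are unaffected. This is a correction worth making to a descriptive safety table before unblinding.

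**What to change.** 1. In SAP 9.2.2, count metabolic syndrome as emergent only in subjects who met fewer than 3 criteria at baseline, and use that group as the denominator.
2. In both tables, replace the Week 1 footnote with the baseline of SAP 9 and 7.1: the last value before first dose. Take it component by component, so that blood pressure comes from Day 1 and lipids, glucose and waist from Screening.
3. Report by arm the number of subjects whose baseline status cannot be determined. The protocol allows a nonfasting sample at screening but requires fasting at Day 21/ET. One sentence should therefore say which components need a fasting value: the syndrome table labels only glucose as fasting, while SAP Appendix 2 also labels triglycerides and HDL.

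The cost is SAP wording and table shells, with no new visits or samples. The downside is a somewhat smaller denominator.
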